10 ABBREVIATIONS

The following is a list of abbreviations that may be used in the protocol.

Table 10-1 Abbreviations

Abbreviation	Term
AE	Adverse Event
BDR	Blinded Data Review
CRS	Clinical Research Scientist

Property of Haleon- Confidential

May not be used, divulged, published or otherwise disclosed without the consent of Haleon

CCI [REDACTED] Abbreviated Clinical Protocol Template v1.0

Abbreviation	Term
eCRF	Electronic Case Report Form
eDiary	Electronic Diary
eICF	Electronic Informed Consent Form
ePRO	Electronic Patient Reported Outcome
EDC	Electronic Data Capture
e.g.	exempli gratia (for example)
GCP	Good Clinical Practice
IB	Investigator's Brochure
ICH	International Conference on Harmonisation
ID	Identification
IRB	Institutional Review Board
IoMT	Internet of Medical Things
ITT	Intention-To-Treat
MAOI	Monoamine Oxidase Inhibitors
mITT	Modified Intention-to-Treat
MCID	Minimal Clinically Important Difference
MFI	Multidimensional Fatigue Index
mg	milligrams
MMRM	Mixed Model with Repeated Measures
N/A	Not Applicable
PDF	Portable Document Format
PP	Per Protocol
QoL	Quality of Life
RWE	Real World Evidence
SAE	Serious Adverse Event
SAP	Statistical Analysis Plan
SP	Safety Population
SUSAR	Suspected Unexpected Serious Adverse Event
UK	United Kingdom
US	United States
Wi-Fi	Wireless Fidelity
Yr	Years

Property of Haleon- Confidential

May not be used, divulged, published or otherwise disclosed without the consent of Haleon

CCI [REDACTED] Abbreviated Clinical Protocol Template v1.0

The purpose of this Statistical Analysis Plan is to describe the planned analyses and outputs to be included in the Clinical Study Report for Protocol 300217.

2 Summary of Key Protocol Information

The purpose of this trial is to demonstrate the efficacy and safety of Emergen-C Core Super Orange Powder to improve the symptoms of fatigue and quality of life (QoL). Efficacy will be demonstrated as superiority of the intervention vs. control group on the QoL assessments at 12 weeks. Safety will be demonstrated through comparison of intervention vs. control groups on incidence of treatment-emergent adverse events (TEAEs).

The study will follow a randomized, double-blind, parallel group, placebo-controlled, decentralized design with two treatment arms. After a screening period, subjects will be randomized to receive Emergen-C Core Super Orange Powder or a placebo according to a pre-specified randomization scheme.

2.1 Study Design

This is a randomized, double-blind, parallel group, placebo-controlled, decentralized clinical trial in healthy male and female subjects, aged 18-64 years, evaluating the over-time effects of 12-weeks daily-use of Emergen-C. Approximately 430 people, aged 18-64 years, will be screened for eligibility. The study expects to enroll about 300 eligible subjects across the United

Haleon Confidential

CCI [REDACTED] Statistical Analysis Plan template v7.0

States. Subjects will be randomized into one of two study groups (at a 1:1 ratio) and will take one sachet of study product (Emergen-C or placebo) once daily in the morning at approximately the same time each day for 12 weeks. A total of approximately 240 subjects are expected to complete the study (approximately 120 in each study group).

Subjects will be recruited through targeted advertising on social media platforms. This study is entirely decentralized, and subjects will not be required to physically attend any on-site visits (only virtual visits). All study data will be collected remotely through a study platform using the subject’s personal mobile device, tablet or computer.

Detailed study procedures can be found in Section 5 of the protocol.

2.2 Study Objectives

Objectives	Endpoints
Primary Objective	Primary Endpoint
To evaluate the effect of daily supplementation with Emergen-C in improving QoL parameters as measured by the Multidimensional Fatigue Inventory (MFI) domains, compared to placebo at Week 12.	Change from Baseline at Week 12 in: 
 • General Fatigue Domain score (items 1,5,12,16) • Physical Fatigue Domain score (items 2,8,14,20) • Reduced Activity Domain score (items 3,6,10,17) • Reduced Motivation Domain score (items 4,9,15,18) • Mental Fatigue Domain score (items 7,11,13,19)
Secondary Objectives	Secondary Endpoints
Efficacy	
To evaluate the effect of daily supplementation with Emergen-C in improving QoL parameters as measured by the MFI domains, compared to placebo at Week 4 and 8.	Change from Baseline at Week 4 and 8 in: 
 • General Fatigue Domain score (items 1,5,12,16) • Physical Fatigue Domain score (items 2,8,14,20) • Reduced Activity Domain score (items 3,6,10,17) • Reduced Motivation Domain score (items 4,9,15,18)

Objectives	Endpoints
	
 • Mental Fatigue Domain score (items 7,11,13,19)
To evaluate the effect of daily supplementation with Emergen-C in improving QoL parameters as measured by the MFI individual items, compared to placebo at Week 4, Week 8 and Week 12.	
 • Change from Baseline at Week 4, Week 8 and Week 12 for each of the individual items in the MFI.
To evaluate the effect of daily supplementation with Emergen-C in improving additional QoL parameters as measured by additional QoL Questions, compared to placebo at Week 4, Week 8 and Week 12.	Change from Baseline at Week 4, Week 8 and Week 12 for: 
 • Family support (Questions 1 and 2 on additional QoL questionnaire) • Resilience (Questions 3 and 4 on additional QoL questionnaire) • Ability to relax and unwind (Questions 5 and 6 on additional QoL questionnaire)
Safety	
To monitor the safety of the study treatment with daily use for 12 weeks.	
 • The number of TEAEs [1]
Exploratory Objectives	Exploratory Endpoints
To evaluate the effect of daily supplementation with Emergen-C in improving additional QoL parameters as measured by additional QoL Questions, compared to placebo at Week 4, Week 8 and Week 12.	Number of days reported at Week 4, Week 8 and Week 12, for: 
 • Days feeling rundown • Days cancelling plans • Days with cold and flu symptoms • Days of work missed
Subgroup analyses for primary and secondary endpoints.	Subgroup analyses for: 
 • Sex (male and female) • Age (18-34 and 35-64 years)

Footnotes: [1] Further details on safety outcomes and data collected in Section 5.7

2.3 Treatments

The investigational product “Emergen-C Core Super Orange Powder” will be provided to subjects in the intervention group, who are instructed to consume one sachet per day in the morning at approximately the same time each day. Subjects in the control group will receive a

placebo product, to be consumed in the same way as the investigational product. Both study products (treatment and placebo) are packaged in individual, unmarked, identical foil sachets.

2.4 Sample Size Calculation

This study will be conducted in healthy male and female subjects, aged 18-64 years (inclusive), and of any race/ethnicity. No discrimination of any kind (e.g. social class, gender, skin color, ethnicity) should preclude eligible participants from participating in the study. The study will aim to recruit a diverse population representative of the US census.

Sufficient subjects will be screened in order to enroll about 300 eligible subjects (approximately 150 subjects per study group) and approximately 240 subjects are expected to complete the study (approximately 120 subjects per study group, allowing for up to 20% dropouts). Potential participants will be recruited through targeted digital advertising campaigns.

3 Planned Analyses

3.1 Interim Analysis

No interim analysis is planned.

3.2 Final Analyses

The final planned primary analyses will be performed after the completion of the following sequential steps:

1. All subjects have completed the study as defined in the protocol.
2. All required database cleaning activities, including any external data reconciliation, have been completed and database has been locked.
3. All criteria for unblinding the randomization codes have been met and the randomization codes have been distributed.

Haleon Confidential

CCI Statistical Analysis Plan template v7.0

4 Considerations for data analyses and Data Handling Conventions

4.1 Baseline Definition

For all endpoints, the baseline value will be the latest pre-dose assessment with a non-missing value.

4.2 Subgroups/Stratifications

The following subgroups will be constructed and analyzed for primary and secondary analyses as an exploratory outcome:

- Sex (male vs. female subjects)
- Age groups (18-34 years vs. 35-64 years).

4.3 Timepoints and Visit Windows

The timepoints and visits for this study are defined in the Table 1: Schedule of Activities. Any deviation from the study schedule may be reviewed on a case-by-case basis at the Blinded Data Review Meeting (BDRM) to determine whether the data should be excluded from the Per-Protocol (PP) analyses.

Table 1: Schedule of Activities

Visit	Treatment Period					
	Pre-screening	Visit 1 Screening & Baseline	Treatment Initiation	Virtual Visit 2	Virtual Visit 3	Virtual Visit 4
Study Day	Day-7 to Day -2	Day -7 to Day -2	Day 1	Week 4 Day 28 (+5)	Week 8 Day 56 (+5)	Week 12 Day 84 (+5)
Medical/Medication History ^a	X					
Demographics ^a	X					
MFI ^a	X			X	X	X
Informed Consent	X					

Haleon Confidential

CCI Statistical Analysis Plan template v7.0

Visit	Treatment Period					
	Pre-screening	Visit 1 Screening & Baseline	Treatment Initiation	Virtual Visit 2	Virtual Visit 3	Virtual Visit 4
Study Day	Day-7 to Day -2	Day -7 to Day -2	Day 1	Week 4 Day 28 (+5)	Week 8 Day 56 (+5)	Week 12 Day 84 (+5)

ID Verification		X				
Inclusions/Exclusion criteria ^c		X				
Eligibility Assessment		X				
Randomization		X				
Participant Training		X				
Study Product Shipped		X				
Supplementary QOL questionnaire		X	X	X	X	X
Concomitant Medication Check		X		X	X	X
Adverse Event (AE/Serious Adverse Event)	X	X	X	X	X	X
Study Product Administration ^b				X (Daily through Week 12 visit)		
Participant Daily eDiary ^a				X (Daily through Week 12 visit)		
Subject Conclusion/Subject Exit from Study						X

^aSubject-reported (self-reported) assessments.

^bSubject will take the study product in the morning of each day

^cSubject will self-report pregnancy status during Visit 1

5 Data Analysis

Data analysis will be performed by PPD [REDACTED], independent biostatistics consultant CCI [REDACTED], with oversight from Haleon. The statistical analysis software used will be Stata Version 18 or later (StataCorp. 2023. *Stata Statistical Software: Release 18*. College Station, TX: StataCorp LLC).

Prior to database lock and unblinding, a BDRM will be conducted in which various aspects of the trial will be discussed and agreed.

Except as described below, all listings will be produced for all randomized subjects.

5.1 Populations for Analysis

Tables described in this section will be produced for the mITT population, unless otherwise specified.

5.1.1 Subject Disposition

Screen failures are defined as subjects who consent to participate in the clinical study but are not subsequently randomized. An enrolled subject is a subject who has signed the informed consent and is eligible to proceed beyond the screening visit.

The number of screened, enrolled, and randomized subjects will be presented in Table 14.1.1 (see [Appendix 2](#)) and a CONSORT diagram showing the flow of subjects through the study will be produced.

The number and percentage of screen failure subjects (subjects not randomized) with reasons why subjects are not randomized will be displayed. Percentages for screen failure subjects will be based on the total number of subjects screened.

The number and percentage of randomized subjects who complete and discontinue the study, broken down by reason for discontinuation, by study product and overall will also be displayed. The percentages will be based on the number of subjects randomized.

Table 14.1.1 will also present the number and percentage of subjects in each of the defined analysis populations (as defined in [Section 4.1.3](#)) by study product and overall. Percentages will be based on the number of subjects randomized.

Subject disposition will be listed for randomized subjects (Listing 16.2.1.1) by study product displaying:

- Subject number
- Demographic data (age, sex, race, and ethnicity)

- Screening date
- Study product start date and time
- Study product end date, and days of study product use
- Subject status (completer, Yes/No) – completer to be defined as providing MFI at week 12
- Study completion /withdrawal date
- Duration (in days) in the study (defined as [(date of completion or withdrawal – start date of study product) + 1]
- Primary reason for withdrawal, if applicable.

Subject disposition information will be listed for all screened, non-randomized subjects (Listing 16.2.1.2), displaying:

- Subject number
- Demographic information (age, sex, race and ethnicity)
- Screening date
- Reason for screen failure
- Any further details of reason for screen failure.

5.1.2 Protocol Deviations

Protocol deviations will be tracked by the study team throughout the conduct of the study. Data will be reviewed prior to unblinding and database lock to ensure all important deviations are captured and categorised. Subjects with important protocol deviations liable to influence the efficacy outcomes will have their affected data excluded from the PP analyses. Subjects may also be identified as having important protocol deviations not leading to exclusion of data from the PP analyses.

Important deviations of the protocol procedures may include, but will not necessarily be limited to the following:

- Consent procedures
- Inclusion/Exclusion criteria
- Concomitant medication/therapy
- Study procedures

Haleon Confidential

CCI [REDACTED] Statistical Analysis Plan template v7.0

- Randomization procedures
- Study drug dosing/study product administration/study product compliance
- Visit schedule/interval
- Other

The assessment process will be specified in the Blind Data Review Plan and subjects with important protocol deviations will be identified at the BDRM.

For all randomized subjects, Table 14.1.2 will present the number and percentage, by study product and overall, and Listing 16.2.2.1 will list:

- Subjects with at least one important protocol deviation
- Subjects with important protocol deviations not leading to exclusion from PP population with reasons for deviations and reasons why the deviation was not excluded from PP population
- Subjects with important protocol deviations leading to exclusion from the PP population with reasons for deviations.

All protocol deviations collected on the protocol deviation case report form page will be listed in Listing 16.2.2.2. The listing will present date of deviation, type of deviation, and deviation description.

5.1.3 Analysis Populations

Three analysis populations are defined.

Population	Definition / Criteria	Analyses Evaluated
Safety	
 • Comprise of all subjects who receive at least one dose of study product. • This population will be based on the treatment the subject actually received. 	
 • Safety
Modified Intent-To-Treat (mITT)	
 • Comprise of all randomized subjects with completed baseline visit (visit 1), at least one completed post-baseline MFI domain assessment, and taken at least one dose of allocated product. • This population will be based on the treatment to which the subject was randomized. 	
 • Demographics • Baseline Characteristics • Efficacy • Subgroup analyses

Population	Definition / Criteria	Analyses Evaluated
	
 Any subject who receives a randomization number will be considered to have been randomized. 	
Per-Protocol (PP)	
 Comprised of all subjects in the mITT population who have adhered to treatment regime and were not affected by protocol deviations. 	
 Sensitivity (Primary endpoint)

Note: Please refer to [Appendix 1](#): List of Data Displays which details the population to be used for each display being generated.

The numbers of subjects included in each of the analysis populations will be summarized (Table 14.1.1). Subjects excluded from any of the analysis populations will be listed in Listing 16.2.3.1, with the reason for exclusion.

The primary population for assessment of efficacy will be the mITT Population. A PP analysis will be performed for efficacy analysis of the primary endpoint if at least 10% of the mITT subjects are excluded from the PP Population. Efficacy data determined to have been potentially impacted by a protocol deviation will be excluded from the PP analysis. A decision on whether a protocol deviation impacts efficacy data and whether to perform a PP analysis will be made at the BDRM.

5.2 Subject Demographics and Other Baseline Characteristics

Demographic and baseline characteristics summaries will be produced for the mITT.

5.2.1 Demographic Characteristics

Demographic and baseline characteristics for each group will be reported for the mITT and Safety populations (and for the PP population, if a PP analysis is performed) using descriptive statistics. Categorical demographic variables are sex, smoking status and race. These variables will be summarized by the number and percentage of subjects with each relevant characteristic in each treatment group. Continuous variables (age, weight, and height) will be summarized by the arithmetic mean, standard deviation, median, minimum, and maximum values in each treatment group. All demographic information will be tabulated (Table 14.1.3.1) and listed (Listing 16.2.4.1).

5.2.2 General Medical History

Medical history/current medical conditions will be listed (see Listing 16.2.4.2) based on self-reported relevant medical and/or surgical history (in the previous 12 months), including allergies or drug sensitivity and prior medications/treatments, including prescription and non-

Haleon Confidential

CCI Statistical Analysis Plan template v7.0

prescription drugs, dietary supplements and herbal remedies, that began before obtaining informed consent.

The presence/absence of any relevant medical history will also be listed in Listing 16.2.4.2, with start date and end date or ongoing at the start of study product.

5.3 Treatments (Study Product, other Concomitant Therapies, Compliance)

Compliance data will be summarized for the mITT population. Exposure and other medications will be summarized on the safety population.

For all randomized subjects, randomization details will be listed, including the randomization number, the planned study product, the actual study product the subject received, and the randomization date (Listing 16.1.7.1).

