8.3.7 Study Product Compliance and Use of Other Therapies

8.3.7.1 Study Product Compliance

Treatment compliance will be assessed daily during the 12-week treatment period. Compliance will be analyzed descriptively by reporting the absolute and relative frequency of subjects with 80% compliance to treatment per block of 4 treatment weeks and overall, for each group. A compliance score will be calculated for each subject by dividing the number of days the allocated treatment was taken by the number of days the treatment was allocated. The compliance score will be summarized for each group and compared between groups.

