5.3.1 Study Product Compliance and Exposure

Treatment compliance will be assessed daily during the 12-week treatment period – the end of the treatment period will be defined as the completion of the last virtual visit 4 MFI questionnaire. If the virtual visit 4 MFI questionnaire is not completed, the date used as the definition will be the treatment initiation date plus 84 days. Both definitions have an acceptable window of +/- 5 days. Compliance will be analyzed descriptively by reporting the absolute and relative frequency of subjects with 80% compliance to treatment per block of 4 treatment weeks and overall, for each group. A compliance score will be calculated for each subject by dividing the number of days the allocated treatment was taken by the number of days the treatment was allocated. The compliance score will be summarized for each group and compared between groups.

Additional information on number of doses taken, number of missed doses, number of expected doses, and dose compliance will be presented both in Table 14.2.1.1 and Listing 16.2.5.1 where:

- Number of doses taken is defined as:
 - Overall: Number of times daily diary indicates a dose was taken between treatment initiation and Week 12 MFI completion date. If the virtual visit 4 MFI questionnaire is not completed, the date used as the definition will be the treatment initiation date plus 84 days.
 - Treatment Start to Week 4: Number of times daily diary indicates a dose was taken between treatment initiation and Week 4 MFI completion date. If the virtual visit 2 MFI questionnaire is not completed, the date used as the definition will be the treatment initiation date plus 28 days.
 - Week 4 to Week 8: Number of times daily diary indicates a dose was taken between Week 4 MFI completion date and Week 8 MFI completion date. If the

Haleon Confidential

CCI Statistical Analysis Plan template v7.0

- virtual visit 3 MFI questionnaire is not completed, the date used as the definition will be the treatment initiation date plus 56 days.
- Week 8 to Week 12: Number of times daily diary indicates a dose was taken between Week 8 MFI completion date and Week 12 MFI completion date. If the virtual visit 4 MFI questionnaire is not completed, the date used as the definition will be the treatment initiation date plus 84 days.
-
- Number of expected doses is defined as:
 - Overall: Week 12 MFI Completion Date - Treatment Start Date.

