14.2 Efficacy Data Summary Tables and Figures					
	Table	Summary of Product Compliance	mITT Population	14.2.1.1.1	---
	Table	Summary of MFI Domain Scores	mITT Population	14.2.2.1.1	Yes
	Table	Summary of MFI Individual Item Scores	mITT Population	14.2.3.1.1	Yes
	Table	Summary of Quality of Life (QoL) Questions (Secondary Endpoint)	mITT Population	14.2.4.1.1	
	Table	Summary of Quality of Life (QoL) Questions (Exploratory Endpoint)	mITT Population	14.2.5.1.1	
	Table	Summary of MFI Domain Scores – Sex Subgroup	mITT Population	14.2.2.1.3	
	Table	Summary of MFI Individual Item Scores– Sex Subgroup	mITT Population	14.2.3.1.3	
	Table	Summary of QoL Questions (Secondary Endpoint) – Sex Subgroup	mITT Population	14.2.4.1.3	
	Table	Summary of MFI Domain Scores – Age Subgroup	mITT Population	14.2.2.1.5	
	Table	Summary of MFI Individual Item Scores– Age Subgroup	mITT Population	14.2.3.1.5	

Haleon Confidential

CCI Statistical Analysis Plan template v7.0

CSR Section	TLF	Title	Population	Template	Topline
	Table	Summary of QoL Questions (Secondary Endpoint) – Age Subgroup	mITT Population	14.2.4.1.5	
	Table	Statistical Analysis of Change from Baseline in Multidimensional Fatigue Inventory (MFI) Domains Over Time (MMRM)	mITT Population	14.2.2.1.2	Yes
	Table	Statistical Analysis of Change from Baseline in MFI Individual Item Scores Over Time (MMRM)	mITT Population	14.2.3.1.2	Yes
	Table	Statistical Analysis of Change from Baseline in Quality of Life (QoL) Questions (Secondary Endpoint) Over Time (MMRM)	mITT Population	14.2.4.1.2	
	Table	Statistical Analysis of Change from Baseline in Quality of Life (QoL) Questions (Exploratory Endpoint) Over Time (MMRM)	mITT Population	14.2.5.1.2	
	Table	Statistical Analysis of Change from Baseline in Multidimensional Fatigue Inventory (MFI) Domains Over Time (MMRM) – Sex Subgroup	mITT Population	14.2.2.1.4	
	Table	Statistical Analysis of Change from Baseline in MFI Individual Item Scores Over Time (MMRM) – Sex Subgroup	mITT Population	14.2.3.1.4	
	Table	Statistical Analysis of Change from Baseline in Quality of Life (QoL) Questions (Secondary Endpoint) Over Time (MMRM) – Sex Subgroup	mITT Population	14.2.4.1.4	
	Table	Statistical Analysis of Change from Baseline in Multidimensional Fatigue Inventory (MFI) Domains Over Time (MMRM) – Age Subgroup	mITT Population	14.2.2.1.6	
	Table	Statistical Analysis of Change from Baseline in MFI Individual Item Scores Over Time (MMRM) – Age Subgroup	mITT Population	14.2.3.1.6	

Haleon Confidential

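### Compliance is summarised and compared between arms only in mITT, which leaves out every dosed subject with no post-baseline MFI

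*SAP*

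**What the plan says.** Protocol 8.3.7.1 defines the score without naming a population: "A compliance score will be calculated for each subject by dividing the number of days the allocated treatment was taken", over the days for which it was allocated. SAP 5.3 supplies the population: "Compliance data will be summarized for the mITT population". SAP 5.3.1 then asks for the frequency of "subjects with 80% compliance to treatment per block of 4 treatment weeks and overall, for each group", and adds: "The compliance score will be summarized for each group and compared between groups". No other population is named for that comparison. In Appendix 1 the table titled "Summary of Product Compliance" appears once, for mITT.

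SAP 5.1.3 admits a randomised subject to mITT only with a completed baseline visit, "at least one completed post-baseline MFI domain assessment, and taken at least one dose of allocated product". The Safety population has no questionnaire requirement: "Comprise of all subjects who receive at least one dose of study product".

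SAP 5.3 also promises that "Exposure and other medications will be summarized on the safety population". However, 5.3.1 defines no separate exposure measure, and Appendix 1 contains no exposure table.

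On dates, SAP 5.3.1 closes the count of doses taken at the MFI completion date or, if that MFI is missing, at treatment start plus 28, 56 or 84 days. The expected-dose definitions use MFI completion dates alone and state no fallback.

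**The concern.** Completing a first post-baseline MFI happens after randomisation. A compliance figure restricted to people who did so describes those who stayed long enough to answer, not everyone who started the product. Early leavers are likely to have the lowest 12-week compliance, and they drop out of numerator and denominator together.

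Two outputs are at stake. One is the reported level of compliance, which matters in a trial meant to show what sustained daily use does in a real-world setting. The other is the between-arm comparison. If one arm loses more people in the first weeks, for instance through taste or tolerability, the comparison is made on what is left and does not reflect that loss. No other planned by-arm summary of product use covers all dosed subjects, because the exposure summary promised on the Safety population has no display behind it.

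**Working it through.** **1. Who reaches the compliance table.** Applying SAP 5.1.3 and 5.3 to three kinds of dosed subject:

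| Subject | Safety | mITT | In compliance table |
|---|---|---|---|
| Stops product early, stays in the study, completes an MFI (Protocol 9.3 asks for this) | yes | yes | yes, as a low complier |
| Stops product and leaves before the first MFI | yes | no | no |
| Keeps dosing but never completes a post-baseline MFI (Protocol 5 lets subjects with missed questionnaires continue) | yes | no | no |

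The second row drives any upward bias. The third row works against it.

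**2. The plan's own figures.** The documents give no compliance rate and no rate of loss before the first MFI. The nearest figure is the maximum dropout of 20% (Protocol 8.1), which reproduces: 240 / (1 − 0.20) = 300 randomised. It covers dropout at any time, so f = 20% would need every planned dropout to leave before a first MFI.

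**3. Model.** Inputs, all assumed:
- f: share of dosed subjects with no post-baseline MFI.
- Cm: mean compliance in mITT, 85–95%.
- d: days on product before leaving, 7–28. Excluded subjects dose at rate Cm until day d and then not at all.
- Denominator: 84 days for everyone.

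Mean over all dosed = (1 − f) × Cm + f × Cm × d/84.

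Overstatement = f × Cm × (1 − d/84).

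Example with Cm = 90%, d = 14, f = 10%: an excluded subject scores 0.90 × 14/84 = 15.0%. The all-dosed mean is 0.90 × 90 + 0.10 × 15 = 82.5%, so mITT overstates it by 7.5 points.

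| f | All-dosed mean (Cm = 90%, d = 14) | Overstatement over Cm 85–95%, d 7–28 |
|---|---|---|
| 0 | 90.0% | 0 |
| 2% | 88.5% | 1.1–1.7 points |
| 5% | 86.2% | 2.8–4.4 points |
| 10% | 82.5% | 5.7–8.7 points |
| 20% (every planned dropout leaves before the first MFI) | 75.0% | 11.3–17.4 points |

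**4. Between arms.** With Cm = 90% and d = 14 in both arms, but f = 5% in one and 15% in the other:
- 0.95 × 90 + 0.05 × 15 = 86.25%
- 0.85 × 90 + 0.15 × 15 = 78.75%

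The arms differ by 7.5 points among all dosed subjects. In mITT both show 90%.

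**5. The 80% threshold.** Over 84 days, a subject gone by the end of the Week 4 window (28 + 5 = 33 days) can reach at most 33/84 = 39.3%. If a share p of mITT reaches 80%, the all-dosed share is p × (1 − f) and the gap is p × f. For p assumed at 80–90%, that is 4.0–4.5 points at f = 5% and 8–9 points at f = 10%.

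**6. The denominator.** Steps 3 to 5 assume 84 expected days. The expected-dose definitions in SAP 5.3.1 do not secure this for a subject without the relevant MFI. If allocated days were instead cut at withdrawal, an early leaver could score near 100% and the gap would vanish. The same hole already affects mITT subjects who have a Week 4 MFI but no Week 12 MFI.

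**The case against.** The strongest reply is that early stopping is reported elsewhere. Table 14.1.1 tabulates completion and discontinuation by reason and by arm with all randomised subjects as denominator. It also gives the size of each analysis population by arm, so the gap between Safety and mITT can be read off. Listing 16.2.3.1 gives exclusions with reasons, Listing 16.2.1.1 gives days of product use, and Listing 16.2.5.1 gives compliance for all randomised subjects. This stands. A reader might infer that unequal early stopping is hidden, and the documents do not support that. What remains is narrower: the listings are subject by subject, and no by-arm summary says how much product these people took.

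A reader might also infer that the SAP made an undeclared change. It did not: Protocol 8.3.7.1 names no population and Protocol 8.3 leaves detail to the SAP.

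Nor can one say that the SAP's own rule puts every excluded subject below 80%. The 84-day fallback is attached to the end of the treatment period and to doses taken, not to expected doses, and a subject without an MFI may still be dosing and completing the eDiary.

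Finally, compliance in the efficacy population is a legitimate description of adherence behind the efficacy estimate. That justifies keeping the mITT table, but not having it as the only one.

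**Conclusion.** The point holds in a limited form. The only compliance summary, and the only between-arm comparison of compliance, rest on a set selected after randomisation that excludes dosed subjects with no post-baseline MFI. It would go too far to say that reported compliance is too high as a matter of fact. That is so only if such subjects exist and mostly stopped early.

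The size cannot be fixed from the documents. Under the stated assumptions it is nil at f = 0, about 3–4 points of mean compliance at f = 5% and 6–9 points at f = 10%. The 20% row is a limiting case, since the plan's dropout allowance covers all 12 weeks. Compliance is a descriptive output and the mITT compliance table does not alter the primary test, so this is a moderate reporting matter.

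**What to change.** - **SAP 5.3 and Appendix 1:** add a by-arm compliance summary and between-group comparison on the Safety population. Keep the mITT table as support for the efficacy results.
- **SAP 5.3.1:** give expected doses the same fallback as doses taken, namely treatment start plus 28, 56 or 84 days when the corresponding MFI is missing. Without this, a Safety table would add subjects who have no defined denominator. It also settles the score for mITT subjects with a missing MFI.

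The cost is a few lines of SAP text and one extra run of a planned table on eDiary data already collected. The downside is that the reported compliance figure may become less favourable.
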